8.3. Adverse Events and Serious Adverse Events

Adverse events will be reported by the participant.

The investigator and any qualified designees are responsible for detecting, documenting, and recording events that meet the definition of an AE or SAE and remain responsible for following up AEs that are serious, considered related to the study intervention or study procedures, or that caused the participant to discontinue the study intervention or study.

Discontinuation information is in Section 7.

Detailed AE definitions and procedures are in Section 10.3.

8.3.1. Time Period and Frequency for Collecting AE and SAE Information

All AEs and SAEs will be collected from the time of signing of the ICF until participation in the study has ended.

Adverse events that begin before the start of study intervention but after signing of the ICF will be recorded on the Adverse Event CRF.

Although all AEs after signing the ICF are recorded by the site in the CRF/electronic data entry, SAE reporting to sponsor begins after the participant has signed the ICF and has received study intervention. However, if an SAE occurs after signing the ICF, but prior to receiving study intervention, it needs to be reported within the SAE reporting time frame if it is considered reasonably possibly related to study procedures.

All SAEs will be recorded and reported to the sponsor or designee immediately and under no circumstance should this exceed 24 hours, as indicated in Section 10.3, Appendix 3. The investigator will submit any updated SAE data to the sponsor within 24 hours of it being available.

Investigators are not obligated to actively seek AEs or SAEs after conclusion of the study participation. However, if the investigator learns of any SAE, including a death, at any time after a participant has been discharged from the study, and he/she considers the event to be reasonably related to the study intervention or study participation, the investigator must promptly notify the sponsor.

8.3.2. Method of Detecting AEs and SAEs

The method of recording, evaluating, and assessing causality of AE and SAE and the procedures for completing and transmitting SAE reports are provided in Section 10.3.

Care will be taken not to introduce bias while detecting AEs and/or SAEs. Open-ended and nonleading verbal questioning of the participant is the preferred method to inquire about AE occurrences.

8.3.3. Follow-up of AEs and SAEs

After the initial AE/SAE report, the investigator is required to proactively follow each participant at subsequent visits/contacts. All SAEs will be followed up until resolution, stabilization, the event is otherwise explained, or the participant is lost to follow-up (as defined in Section 7.3). Further information on follow-up procedures is provided in Section 10.3.

8.3.4. Regulatory Reporting Requirements for SAEs

Prompt notification by the investigator to the sponsor of an SAE is essential so that legal obligations and ethical responsibilities toward the safety of participants and the safety of a study intervention under clinical investigation are met.

The sponsor has a legal responsibility to notify both the local regulatory authority and other regulatory agencies about the safety of a study intervention under clinical investigation. The sponsor will comply with country-specific regulatory requirements relating to safety reporting to the regulatory authority, IRB/IEC, and investigators.

An investigator who receives an investigator safety report describing an SAE or other specific safety information (e.g., summary or listing of SAEs) from the sponsor will review and then file it with the IB, and will notify the IRB/IEC, if appropriate according to local requirements.

8.3.5. Pregnancy

Details of all pregnancies in female participants and female partners of male participants will be collected after the start of study intervention and until at least 5 months after the last dose.

If a pregnancy is reported, the investigator should inform the sponsor within 24 hours of learning of the pregnancy and should follow the procedures outlined in Section 10.4.

Abnormal pregnancy outcomes (e.g., spontaneous abortion, fetal death, stillbirth, congenital anomalies, ectopic pregnancy) are considered SAEs.

8.3.6. Hypersensitivity Reactions

Many drugs, but particularly biologic agents, carry the risk of systemic hypersensitivity reactions. If such a reaction occurs, additional details describing each symptom should be provided to the sponsor in the infusion-related reaction/hypersensitivity CRF.

If symptoms and/or signs occur during or within 6 hours after end of infusion of LY3832479 and are believed to be hypersensitivity or due to cytokine release, then investigators are encouraged to report the event as infusion-related immediate hypersensitivity reaction or cytokine release-associated infusion reaction, respectively.

Sites should have appropriately trained medical personnel and appropriate medical equipment available when study participants are receiving intervention. It is recommended that participants who experience a systemic hypersensitivity reaction be treated per national and international guidance (Lieberman et al 2015; Simons et al. 2015)

In the case of generalized urticaria or anaphylaxis, additional blood and urine samples should be collected as described in Section 10.7, Appendix 7, "Recommended Laboratory Testing for Hypersensitivity Events". Laboratory results are provided to the sponsor via the central laboratory.

8.3.7. SARS-CoV-2 Infection

In the event of a suspected SARS-CoV-2 infection, participants will undergo a viral test using nasal or nasopharyngeal swab and be managed according to standard of care.

Suspicion of SARS-CoV-2 infection, in the opinion of the investigator, will rely upon

- a recent exposure to SARS-CoV-2 defined as:
 - living in the same household as a person with SARS-CoV-2;
 - having had direct physical contact with a person with SARS-CoV-2 (e.g. shaking hands);
 - having unprotected direct contact with infectious secretions of a person with SARS-CoV-2 (e.g. being coughed on, touching used paper tissues with a bare hand);
 - having had face-to-face contact with a person with SARS-CoV-2, within 2 m and for more than 15 minutes.
- and/or signs or symptoms that, in the opinion of the investigator, are suggestive of SARS-CoV-2 infection (e.g., fever, dry cough, shortness of breath, hypoxia, etc.)

In addition, SARS-CoV-2 point-of-care tests may be performed at specific timepoints during the study at the discretion of the investigator. Every time such a point-of-care test is performed post baseline, an additional nasal or nasopharyngeal swab sample may be collected in parallel, for research purposes such as viral sequencing. This research swab sample will be shipped to the sponsor only if the point-of-care test is positive. If the point-of-care test is negative, the research swab sample should be discarded.

If any participant is tested positive post baseline, prior to this protocol amendment being approved, an additional nasal or nasopharyngeal swab sample may be collected for research purposes.

8.3.8. Infusion-Related Reactions

As with other mAbs, infusion-related reactions may occur during or following LY3832479 administration. If an infusion-related reaction occurs, additional data describing each symptom and sign should be provided to the sponsor in the CRF.

This table describes the location of infusion-related reaction information in this protocol.

Topic	Location
Special treatment considerations	Section 6.1.1
Management of infusion reactions	Section 6.1.1.2
DAIDS table describing severity	Section 6.1.1.2
Treatment guidelines for infusion-related reactions	Section 6.1.1.2

Symptoms occurring during or after infusion of study intervention may also be defined according to AE categories such as acute allergic reaction or cytokine release syndrome (refer to DAIDS).

8.3.9. Product Complaints

A product complaint is any written, electronic, or oral communication that alleges deficiencies related to the identity, quality, durability, reliability, safety, effectiveness, or performance of a trial intervention.

The sponsor collects product complaints on study interventions used in clinical studies to ensure the safety of study participants, monitor quality, and to facilitate process and product improvements.

Participants will be instructed to contact the investigator as soon as possible if they have a complaint or problem with the study intervention so that the situation can be assessed.

NOTE: Any AEs or SAEs that are associated with a product complaint will follow the processes outlined in Section 8.3.3 and Appendix 10.3 of the protocol.

Time Period for Detecting Product Complaints

Product complaints that result in an AE will be detected, documented, and reported to the sponsor during all periods of the study in which the study intervention is used.

If the investigator learns of any product complaint at any time after a participant has been discharged from the study, and such incident is considered reasonably related to the study intervention, the investigator will promptly notify the sponsor.

Prompt Reporting of Product Complaints to Sponsor

Product complaints will be reported to the sponsor within 24 hours after the investigator becomes aware of the complaint.

The Product Complaint Form will be sent to the sponsor by a method designated by the sponsor.

Follow-up of Product Complaints

Follow-up applies to all participants, including those who discontinue study intervention.

The investigator is responsible for ensuring that follow-up includes any supplemental investigations as indicated to elucidate the nature and/or causality of the product complaint.

New or updated information will be recorded on the originally completed form with all changes signed and dated by the investigator and submitted to the sponsor.

8.4. Treatment of Overdose

For the purposes of this study, an overdose of LY3832479 is considered any dose higher than the dose assigned through randomization. In case of suspected overdose, participants should be monitored for any signs or symptoms of adverse reactions or effects, and supportive care should be provided as necessary.

8.5. Pharmacokinetics

Venous blood samples will be collected as specified in the SoA for determination of serum concentrations of LY3832479 used to evaluate the PK for LY3832479.

A maximum of 5 samples may be collected at additional time points during the study if warranted and agreed upon between the investigator and the sponsor.

Instructions for the collection and handling of biological samples will be provided by Lilly.

Site personnel will record

- the date and time (24-hour clock time) of administration (start and end of infusion), and
- the date and time (24-hour clock time) of each PK sample.

It is essential that the times are recorded accurately.

8.6. Pharmacodynamics

Pharmacodynamic parameters are not evaluated in this study.

8.7. Genetics

A whole blood sample will be collected for pharmacogenetic analysis where local regulations allow.

See Section 10.2 Clinical Laboratory Tests, and Section 1.3 SoA for sample collection information.

See Section 10.5 for genetic research, custody, and sample retention information.

8.8. Biomarkers

Blood samples will be collected from all participants for analysis of immune system and LY3832479-related markers. Serum samples for exploratory biomarker research will be collected at the time specified in the SoA where local regulations allow.

Samples will be stored and analysis may be performed on biomarkers thought to play a role in immune system-related responses to viral infection or administration of LY3832479 including, but not limited to, immune pathways or serum analytes to evaluate their association with LY3832479 administration.

Samples may be used for research to develop methods, assays, prognostics, and/or companion diagnostics related to the intervention target (S protein), pathways associated with disease, and/or the mechanism of action of the study intervention.

Post-baseline swab samples may be used for research purposes, such as viral sequencing.

Sample retention is described in Section [10.1.10](#).

8.9. Immunogenicity Assessments

Visits and times

At the visits and times specified in the SoA, predose venous blood samples will be collected to determine antibody production against LY3832479. The actual date and time (24-hour clock time) of each sample collection will be recorded. To aid interpretation of these results, PK samples will be collected at the same time points as the immunogenicity samples.

Sample collection, handling, and use

Instructions for the collection and handling of blood samples will be provided by the sponsor.

Immunogenicity will be assessed using a validated assay designed to detect ADAs in the presence of LY3832479 at a laboratory approved by the sponsor. Antibodies may be further characterized for their ability to neutralize the activity of LY3832479.

Sample retention

Sample retention is described in Section [10.1.10](#).

8.10. Health Economics

Not applicable.

9. Statistical Considerations

9.1. Statistical Hypotheses

This is an exploratory study with a primary objective of assessing safety and tolerability. Any hypothesis tests conducted for treatment comparisons will be exploratory in nature and conducted without adjustment for multiplicity.

9.2. Sample Size Determination

A maximum of 30 participants will be enrolled to study intervention such that approximately 8 participants have sufficient evaluable data in each cohort.

The sample size is customary for first-in-human studies evaluating safety and PK, and is not powered on the basis of statistical hypothesis testing.

For replacement of participants who are randomized but not dosed, see Section [4.1.1](#).

9.3. Populations for Analyses

The following populations are defined:

Population	Description
Entered	All participants who sign the ICF
Safety	All participants randomly assigned to study intervention and who are administered at least 1 dose of study intervention. Participants will be analyzed according to the intervention they actually received.
Pharmacokinetic Analysis	All randomized participants who received study intervention and have baseline and have multiple evaluable PK samples.

9.4. Statistical Analyses

Statistical analysis of this study will be the responsibility of sponsor or its designee.

All tests of treatment effects will be conducted at a 2-sided alpha level of 0.05, unless otherwise stated, and all confidence intervals will be given at a 2-sided 95% level.

Any change to the data analysis methods described in the protocol will require an amendment only if it changes a principal feature of the protocol. Any other change to the data analysis methods described in the protocol, and the justification for making the change, will be described in the statistical analysis plan (SAP) and the clinical study report. Additional exploratory analyses of the data will be conducted as deemed appropriate.

The SAP will be finalized prior to unblinding and it will include a more technical and detailed description of the statistical analyses described in this section. This section is a summary of the planned statistical analyses of the most important endpoints including primary and key secondary endpoints.

9.4.1. General Considerations

Statistical analyses will be performed using SAS® Version 9.4 or higher.

For continuous measures, summary statistics will include sample size, mean, standard deviation, minimum, median, and maximum. For categorical measures, summary statistics will include the sample size, frequency count, and percentage.

For all safety analyses, baseline will be defined as the last evaluable value before dosing.

9.4.2. Primary Endpoints (Safety)

All analyses of primary endpoints will be made on the Safety Population.

All investigational product- and protocol procedure-related AEs will be listed and, if the frequency of events allows, safety data will be summarized using descriptive methodology. The incidence of symptoms for each treatment will be presented by severity and by association with investigational product as perceived by the investigator.

A TEAE is defined as an event that emerges after treatment (ie, after administration of placebo or LY3832479), having been absent pretreatment, or worsens relative to the pretreatment state.

The number of participants who experience a TEAE and/or an SAE (all causalities and related to study drug) will be summarized by study treatment. All TEAEs will be summarized by system organ class and by decreasing frequency within system organ class.

Other safety parameters that will be assessed include safety laboratory parameters, vital signs, and ECG parameters. The parameters will be listed and summarized using summary statistics. Additional analysis will be performed if warranted upon review of the data.

9.4.3. Secondary Endpoints (PK)

Pharmacokinetic parameter estimates for LY3832479 will be calculated using standard noncompartmental methods of analysis and summarized by dose using descriptive statistics, if sufficient data are available.

The parameters for analysis will be Cmax and AUC of LY3832479. Other noncompartmental parameters, such as time to Cmax, apparent terminal elimination half-life, clearance, and volume of distribution may be reported. Analyses of other PK parameters may be performed, if appropriate.

A compartmental analysis may also be performed to further characterize LY3832479 PK and support model-based PK simulations.

9.4.4. Tertiary/Exploratory Endpoint (Immunogenicity)

The frequency and percentage of participants with preexisting ADA and treatment-emergent (TE) ADA+ to LY3832479 will be tabulated. Treatment-emergent ADA+ is defined as those with a titer 2-fold (1 dilution) greater than the minimum required dilution if no ADAs were detected at baseline (treatment-induced ADA) or those with a 4-fold (2 dilutions) increase in titer compared to baseline if ADAs were detected at baseline (treatment-boosted ADA). For the TE ADA+ participants, the distribution of maximum titers will be described. The frequency of neutralizing antibodies may also be tabulated in ADA+ participants.

The relationship between the presence of antibodies to LY3832479 concentrations/PK parameters, and/or safety assessment may be assessed.

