4.3. Justification for Dose

The dose levels for this study are designed to explore a wide exposure range that potentially encompasses the therapeutic dose, and will provide the safety and tolerability underpinnings for the clinical drug development plan for LY3832479. Due to the uncertainty of in vitro to in vivo translation and uncertainty in translation of data from a rhesus macaque SARS-CoV-2 infection model to humans, 3 methods were utilized to predict an efficacious human dose range of 2000 to 7000 mg.

The first method involved identifying a human dose that would, in the majority of patients (more than 90%), achieve trough lung concentrations (Day 28 after dosing) greater than the concentration that was found to neutralize 90% of the virus (IC90) in vitro. This approach used the human PK as projected from the monkey TK study and incorporated drug distribution into lung tissue (Shah and Betts 2013; Magyarics et al. 2019). This approach identified a dose of 2000 mg.

The second method involved developing a semi-mechanistic SARS-CoV-2 viral dynamic model (Kim et al. 2020) as adapted from a typical viral dynamic model (Cangelosi et al. 2018). This method aimed to identify a dose that would result in the most rapid clearance of virus from a patient and identified a dose of 3000 mg.

The third method was to find a dose that would achieve human serum concentrations throughout a 28-day dosing interval equivalent to serum concentrations in a successful rhesus macaque SARS-CoV-2 challenge study. This method identified that a dose of 7000 mg may be required.

The projected human half-life of LY3832479, based on allometric scaling from monkey data, is expected to be in the 2- to 4-week range.

Safety margins for the proposed starting and maximum dose in this study are shown in [Table 4.1](#).

The proposed starting human dose of 700 mg has a 10-fold margin of safety for evaluation of safety, tolerability, and PK based on expected exposure (AUC) relative to the maximum tested dose in a single-dose monkey toxicity/TK study. The subsequent doses of 2800 and 7000 mg in the single-ascending dose cohorts are planned to be administered following interim safety data from the previous cohorts as described in [Section 6.6](#). The highest proposed dose, 7000 mg, would have a 1x margin of safety. This margin of safety is considered acceptable for the following reasons:

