- LY3832479 is a mAb directed against a foreign target and was isolated from a convalescent patient with COVID-19. Therefore, the test article does not bind to antigens/targets expressed in human tissues as confirmed by a GLP-complaint TCR study in human tissues, representing a low risk for potential on-target or off-target toxicity.
- The 1x exposure-based margin for 7000 mg is based on the maximum dose tested in monkeys in the single-dose toxicology/TK study. Based on clinical observations and gross examination at necropsy, no toxicity was observed in the animals administered 186 mg/kg of LY3832479 (final report pending).
- The risk of infusion-related reaction is considered low due to the target, the reduced effector function (Fc and Complement binding), and the human origin of this antibody.
- The engineered LALA mutations are expected to reduce Fc effector function in LY3832479 and should reduce the risk of ADE (see [Section 2.2](#)).

Table 4.1. Margin of Safety for Intravenous Administration of LY3832479 Based on Administered Dose and Predicted Exposure

	Dose (mg/kg)	Dose Multiple ^a	AUC _{0-∞} (mg*h/mL) ^a	AUC Exposure Multiple ^a	Cmax (mg/mL)	Cmax Exposure Multiple ^a
Starting human dose^b	10	18.6	75	~10	0.253	~19
Highest human dose^b	100	1.86	753	~1.0	2.51	~1.9
Cynomolgus monkey maximum tested dose^c	186		750		4.75	

Abbreviations: AUC = area under the concentration versus time curve; AUC_{0-∞} = AUC from time zero to infinity; Cmax = maximum drug concentration; NOAEL = no-observed-adverse-effect level.

^a Dose multiple is the dose in animals/dose in humans based on milligrams per kilogram. Exposure multiple is the calculated AUC and Cmax in animals and predicted AUC and Cmax in humans.

^b Assume 70-kg bodyweight.

^c Maximum tested dose in the single-dose monkey toxicology/toxicokinetic study.

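### Section 9.4.4 counts treatment-emergent ADA by titre without using the paired drug concentrations, so the percentage can be biased downward, most at 7000 mg

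*Protocol*

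**What the plan says.** Protocol Section 9.4.4 sets the count: "The frequency and percentage of participants with preexisting ADA and treatment-emergent (TE) ADA+ to LY3832479 will be tabulated". For participants without ADA at baseline the rule is: "Treatment-emergent ADA+ is defined as those with a titer 2-fold (1 dilution) greater than the minimum required dilution if no ADAs were detected at baseline". Participants with baseline ADA need a 4-fold rise in titre. No drug concentration enters either rule. There is no inconclusive class and no stated denominator, and Section 9.3 defines no ADA-evaluable population. The link to concentration is optional: "The relationship between the presence of antibodies to LY3832479 concentrations/PK parameters, and/or safety assessment may be assessed".

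Protocol Section 8.9 does deal with circulating drug at the sampling and assay stage. It specifies a "validated assay designed to detect ADAs in the presence of LY3832479" and adds: "To aid interpretation of these results, PK samples will be collected at the same time points as the immunogenicity samples". It gives no numerical tolerance limit.

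The SAP does not take the matter further. Its Section 3 scope is safety, tolerability and PK. Section 9.4.10 lists, without summarising, any safety assessment not otherwise described. Section 11 declares no changes from the protocol analyses.

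**The concern.** An assay can be validated to find ADA in the presence of drug only up to some concentration. Above it, a not-detected result does not establish that ADA is absent. Under Section 9.4.4 such a result simply joins those that are not treatment-emergent positive. The paired PK samples are collected to help read these results, yet the counting rule never calls on them.

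Immunogenicity is named in the study title, and Protocol Section 2.2 expects ADA formation to be unlikely. A rate near zero at 7000 mg would naturally be read as confirming that expectation, although this is the cohort where a negative result is hardest to interpret.

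**Working it through.** **Inputs.** Protocol Table 4.1: predicted AUC 75 mg·h/mL and Cmax 0.253 mg/mL at 700 mg; 753 and 2.51 at 7000 mg; 750 and 4.75 for the monkey maximum dose. Section 4.3: the projected half-life "is expected to be in the 2- to 4-week range". Section 4.1.1: 7, 7 and 6 active participants in Cohorts 1 to 3. Post-dose ADA visits are read as Days 15, 29, 57 and 85. The Schedule of Activities table is broken, so this is an assumption; it agrees with the five immunogenicity samples in Section 10.2.1. On the same reading there is a PK sample at each of these visits.

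**The plan's own figures.** The Table 4.1 multiples reproduce. AUC: 750/75 = 10.0 and 750/753 = 0.996. Cmax: 4.75/0.253 = 18.8 and 4.75/2.51 = 1.89. The documents state no ADA rate and no tolerance limit to check.

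**Predicted drug at the ADA visits.** The terminal-phase level is at most C(t) = AUC × λ × exp(−λt), with λ = ln 2/half-life and t counted from Day 1. At 7000 mg on Day 85 (t = 84 days):

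- 14-day half-life: λ = 0.002063 per hour and 6 half-lives have passed, so 753 × 0.002063/64 = 0.024 mg/mL.
- 28-day half-life: λ = 0.001031 per hour and 3 half-lives have passed, so 753 × 0.001031/8 = 0.097 mg/mL.

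Ranges over half-lives of 14, 21 and 28 days, in µg/mL:

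| Dose | Day 15 | Day 29 | Day 57 | Day 85 |
|---|---|---|---|---|
| 700 mg | 55–77 | 39–41 | 10–19 | 2.4–9.7 |
| 7000 mg | 549–777 | 388–411 | 97–194 | 24–97 |

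Bi-exponential curves matched to both Cmax and AUC, with an assumed distribution half-life of 1 or 3 days, give similar or slightly lower values (20–89 µg/mL at 7000 mg on Day 85). The 7000 mg level needs log2(10) = 3.3 half-lives, or 47 to 93 days, to fall to the 700 mg level.

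**Number of the four post-dose samples above an assumed tolerance limit.**

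| Assumed limit (µg/mL) | 700 mg | 7000 mg | Day 85 at 7000 mg |
|---|---|---|---|
| 50 | 1 | 3–4 | above only if half-life exceeds about 18 days |
| 100 | 0 | 2–3 | below |
| 200 | 0 | 2 | below |
| 500 | 0 | 1 | below |

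**Bias if masking occurs.** Expected bias = −(true rate) × (1 − share detected). With an assumed true rate of 10% and half detected, 5% is expected (−5 points). With 30% and half detected, 15% is expected (−15 points). With full detection the bias is 0.

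**Precision.** One participant is 100/6 = 16.7 points in Cohort 3 and 100/7 = 14.3 points in Cohorts 1 and 2. The exact 95% upper limit for a zero count is 1 − 0.025^(1/n): 45.9% for 0/6 and 41.0% for 0/7.

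**The case against.** A reader might infer that the protocol overlooks circulating drug, or that the 7000 mg percentage is in fact biased downward. The documents support neither. Section 8.9 specifies an assay meant to work with drug present and pairs PK with ADA sampling. Whether anything is masked depends on a limit that is not given, so the bias runs from zero to the whole true rate.

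Counting samples above a limit also overstates the problem, because Section 9.4.4 counts participants. At three of the four assumed limits the Day 85 sample at 7000 mg is conclusive on predicted levels. What then remains is ADA that appears and disappears before Day 85.

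The protocol defines no negative class and does not say that the table is by dose, so treating non-positives as negatives is a reading of the text. Section 9.4 calls itself a summary and leaves technical detail to the SAP.

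These points limit the size of the concern but do not close the gap. A percentage needs a complement, and the plan gives a masked result nowhere else to go. The deferred detail is not in the SAP. Validating an assay does not tell the analyst how to classify a not-detected result above the validated range.

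**Conclusion.** The concern holds as a gap in the counting rule. The ADA percentage can be biased downward, and any such bias would be largest at 7000 mg, where predicted drug is about ten times the 700 mg level at every ADA visit. Its size cannot be determined from the documents. A limit above about 97 µg/mL would leave the last visit interpretable in all cohorts; a lower one could leave some or all Day 85 results at 7000 mg uninterpretable, depending on the half-life. This rests on the Table 4.1 predictions, the projected half-life and the visit days as read.

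A reader might go on to expect a false dose trend or a falsely reassuring zero. With 6 or 7 active participants per cohort, neither a trend nor a zero could carry much weight, even with perfect detection. The endpoint is exploratory and the primary and secondary objectives are untouched. The small numbers do make it useful to show how many of the six top-dose results can be interpreted.

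**What to change.** In Protocol Section 9.4.4 and in the SAP:

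- State the assay's validated drug-tolerance limit.
- Classify a not-detected post-dose sample as negative only if the paired LY3832479 concentration is at or below that limit, and otherwise as inconclusive.
- Tabulate TE ADA+, TE ADA-negative and inconclusive participants by dose, and state how sample results combine into a participant's class. One simple rule for non-positive participants is to use the last post-dose sample and list inconclusive earlier samples.
- Use all participants with a baseline and at least one post-dose ADA result as the denominator of the main percentage, with the inconclusive count beside it.

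Do not use a denominator that always keeps positives but drops inconclusive non-positives, because it inflates the rate where drug is highest. With 1 positive and 5 inconclusive participants it gives 1/1 = 100%, against 1/6 = 16.7% with 5 shown as inconclusive.

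The paired PK samples are already planned, so the cost is wording and minor programming. The downside is a less reassuring ADA statement at the highest dose if results there prove inconclusive. If the assay tolerates the observed levels, the inconclusive column is empty and the negative finding is stronger.
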